Treatment of Covid-19 With a Herbal Compound, Xagrotin

NCT05017493

ClinicalTrials.gov Submission Date 30- NOVEMBER -2021

Unique Protocol Identification Number: **02-032021-SULXAG/NO**

Protocol Version 1.4.2: 24- NOVEMBER-2021

Study Type: **Interventional**

Record Verification Date: **March, 2021**

Board Approval Number: **118/KRGJUL/CH/ADM/ 09**

Board Name: **Institutional Ethical Committee**

Board Affiliation: **Directorate of health of Sulaimani, Iraq -KRG**

Study start Date: July 1, 2020 [Actual]

Primary Completion Date: December 7, 2020 [Actual]

Study Completion Date: February 8, 2021 [Actual]

Sponsor: Biomad AS

Responsible Party: Sponsor

Collaborators: Directorate of health of Sulaimani, Iraq -KRG

Sample size calculation

The aim of this clinical trial was to evaluate the short-term effects of Xagrotin in improving Covid-19 symptoms in patients as well as reducing mortality in Covid-19 patients.

Out of the 11000 eligible patients, we selected 539 patients. The 539 patients were divided into two groups. The sample size is calculated by following formula:

Parameter	Value
Study population	10000
Confidence interval 95 % (Z)	1.96
Margin of Error (e)	0.05
Uncertainty sample ratio (P)	0.5
Sample ratio	0.05

$$\text{Sample size: } N \times \frac{\frac{Z^2 \times p \times (1-p)}{e^2}}{[N-1 + \frac{Z^2 \times p \times (1-p)}{e^2}]}$$
$$= (10000 \times (1.96^2) \times 0.5 \times (1-0.5)) / (10000 - 1) + (1.96^2) \times 0.5 \times (1-0.5) / (0.05^2)$$

Sample size= 370

To confirm the sufficient sample size of the study, we compared the results of the two groups. Comparison of the results of the two study groups showed that the statistical difference between the two groups was significant (< 0.001). The Pocock boundary and the O'Brien-Fleming boundary consider P-value= 0.02 as strength of evidence to stop a trial for benefit. However, the Haybittle-Peto boundary has shown that if data has a statistical difference at the level of P <0.001, it can be considered as evidence for stopping an early trial for benefit. Most of the results of our study had a P-value <0.001 that allowed us to stop sampling. On the other hand, our results showed a major therapeutic advancement. Given the high mortality rate of Covid-19 in the world, we ethically needed to stop random sampling in current clinical trial study and publish the results as soon as possible.

During the onset of Covid-19 pandemic, the Xagrotin drug has been synthesized and made available continuedly to the indigenous people. Since the initial statistical outcomes showed the

satisfactory results; we have not stopped collecting new data. The new collected data and analysis confirms the previous results.

Randomization and blinding

Among over 11000 eligible Covid-19 patients who had taken Xagrotin for their Covid-19 infections, we randomly selected 361 patients to be included in the study group where 178 eligible Covid-19 patients were randomly recruited to the control group.

Populations and subgroups to be analyzed

-Populations

All randomized study subjects will be included in an “intention to treat” analysis. This will be seen as the primary population for the analysis.

-Analysis

This analysis evaluates the efficiency and safety of Xagrotin, a herbal combination drug, in treatment of patients with covid-19 compared to routine drugs used for coronavirus in hospitals. Statistical analysis was carried out by Statistical Package for the Social Sciences (SPSS, V.23). At first, the Kolmogorov–Smirnov test was used to analyze the distribution normality of data. Data with normal distribution were shown as mean \pm SD. An Independent t-test was used to perform mean comparisons for normally distributed data. Mann-Whitney and Kruskal-Wallis tests were used for the analysis of non-normal data. Correlations between variables were measured using Pearson correlation and Spearman rank correlation tests for normal and non-normal data, respectively, with a 95% confidence interval. Regression analysis was used to evaluate the effect of Xagrotin on the risk of mortality and hospitalization in Covid-19 patients.

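### The SAP's 370 is computed correctly but sizes one proportion in one population; neither it nor the observed P<0.001 shows that a 361 vs 178 comparison is adequately sized

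*SAP*

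**What the plan says.** The SAP, under Sample size calculation, introduces its only calculation with "The 539 patients were divided into two groups. The sample size is calculated by following formula". The inputs are a study population of 10000, Z = 1.96, a margin of error of 0.05 and a proportion of 0.5. A further row, Sample ratio 0.05, is listed but does not enter the formula. The result is "Sample size= 370".

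The same section offers a second ground: "To confirm the sufficient sample size of the study, we compared the results of the two groups". It reports a difference at P<0.001, refers to the Pocock, O'Brien-Fleming and Haybittle-Peto boundaries, and concludes: "Most of the results of our study had a P-value <0.001 that allowed us to stop sampling".

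The arms are 361 (Xagrotin) and 178 (control), 539 in total (Protocol, Study Design; SAP, Randomization and blinding). The Protocol's Outcome Measures table lists 30-day mortality and duration of disease in days as primary outcomes and hospitalization as secondary. The SAP's Analysis text compares the two groups.

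**The concern.** The study compares two groups, but the formula describes a survey of one. A reader who meets 370, a 5% margin and P<0.001 in a section on sample size will take them as evidence that the comparison of 361 with 178 was planned to an adequate size. None of the three bears on that.

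The second ground raises a further issue. The observed result is used both to declare the size sufficient and to justify ending sampling. If sampling ends because the results look good, with no plan for when to look and how far to go, the reported benefit may be a false positive or exaggerated. The SAP's account of its sample size gives the reader no warning of this.

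**Working it through.** **1. Reproduce 370.** Inputs are from the SAP table.

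n0 = Z² × p(1−p) / e² = 1.96² × 0.25 / 0.05² = 384.16

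n = N × n0 / (N − 1 + n0) = 10000 × 384.16 / (9999 + 384.16) = 369.98, so 370.

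The displayed formula therefore gives the stated figure. The substitution line beneath it, as it reads in the text, has misplaced brackets (385.1 if taken literally). That may come from the PDF and nothing here rests on it.

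The text gives 11000 eligible patients where the formula uses 10000. With N = 11000, n = 11000 × 384.16 / (10999 + 384.16) = 371.2, a change of one or two patients.

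**2. What the formula contains.** One population, one proportion, one margin. There is no control rate, target difference, standard deviation, power or allocation ratio. A formula for a proportion cannot size an outcome measured in days.

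**3. Set 370 against the actual numbers.** Single-group 95% margin at p = 0.5 is 1.96 × √(0.25/n), without finite-population correction.

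| Group | n | Relative to 370 | Margin |
|---|---|---|---|
| Xagrotin | 361 | 9 fewer (2.4%) | ±5.2 points |
| Control | 178 | 192 fewer (52%) | ±7.3 points |
| Total | 539 | 169 more (46%) | ±4.2 points |

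**4. Precision of the comparison.** At p = 0.5:

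1.96 × √(0.25/361 + 0.25/178) = 0.0898, or about ±9.0 points.

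The documents give no event rate. Replacing 0.25 by p(1−p) for an assumed common rate p gives ±1.8 points at 1%, ±2.5 at 2%, ±3.9 at 5%, ±5.4 at 10% and ±7.2 at 20%.

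**5. The P-value and the boundaries.** An observed P-value describes data already obtained. It says nothing about whether the size was adequate in advance, so using it as confirmation is circular. A stopping boundary controls error only for a planned set of looks up to a stated maximum size, and neither the Protocol nor the SAP gives either. The SAP says that most results reached P<0.001 without naming them, so a reader cannot tell whether mortality was among them.

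**6. Illustration only.** With 361 vs 178, a fixed sample size and one two-sided 0.05 test, power to detect a halving of an assumed control mortality is about 15–19% from 2%, 30–35% from 5%, 55–58% from 10% and 87–88% from 20%. The ranges span normal-approximation and exact methods. Adequacy for mortality thus turns on a rate that the documents do not supply.

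**The case against.** Several points on the other side stand.

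- The calculation is not an arithmetic error: 370 is correct for what it computes.
- 361 is only 9 short of 370, and 539 exceeds it if 370 is read as a minimum total. Only the control arm is materially short, and only if 370 was meant per arm, which the SAP does not say.
- ±9.0 points is the worst case. At common rates of 5% or below, the absolute margin for the difference is inside 5 points. The SAP never promised ±5 points for a difference, so ±9.0 is not a broken commitment. A narrower margin at low rates does not show adequacy either, because the differences of interest are then also small.
- The power figures rest on assumed rates and a fixed sample size. The SAP's own statement that results allowed sampling to stop contradicts the second assumption, so they can only illustrate.

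A reader might infer that the SAP contradicts itself by stopping sampling and then saying "we have not stopped collecting new data. The new collected data and analysis confirms the previous results". The two can be reconciled: study sampling ended, while data on continuing users of the product were still gathered.

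The source of the patients is less easily reconciled. Sample size calculation says "Out of the 11000 eligible patients, we selected 539 patients". Randomization and blinding says "Among over 11000 eligible Covid-19 patients who had taken Xagrotin for their Covid-19 infections, we randomly selected 361 patients" and then that "178 eligible Covid-19 patients were randomly recruited to the control group", without placing those controls among the 11000. This is mainly a question of selection. It matters here because it leaves unclear which population the formula describes.

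**Conclusion.** The point holds as a fault in the justification of the design, not in the arithmetic. The 370 with its 5% margin answers a different question from the one the study asks, and the observed P<0.001 cannot confirm a sample size. The boundaries named do not repair this without planned looks and a maximum size.

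The size of the gap, at the SAP's own p = 0.5 and treating the arms as independent samples, is a 95% margin of about ±9.0 points for the between-group difference, narrower for rarer outcomes.

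A reader might go further and conclude that 539 patients were too few. The documents do not support that: they give no target difference and no planning event rate or standard deviation against which to judge it. What they show is that neither stated ground demonstrates adequacy, and that stopping on observed results without a documented plan may overstate the benefit. This should be corrected in the SAP text.

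**What to change.** Withdraw 370, the 5% margin and the sentence "To confirm the sufficient sample size of the study, we compared the results of the two groups" as evidence of adequacy, and do not use "Most of the results of our study had a P-value <0.001 that allowed us to stop sampling" as a sample-size justification. Put in their place:

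> No sample size or power calculation for the between-group comparison was made. [Sponsor to correct if one exists, and to state how 361 and 178 arose and whether the controls came from the 11000.] With 361 vs 178 the 95% margin for a difference in proportions is about ±9.0 points at 50%, and narrower for rarer outcomes. Sampling was stopped on the basis of observed results without a prespecified interim plan [sponsor to correct if one existed], so P-values and effect estimates may overstate the benefit.

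Leave retrospective power figures out of the SAP. The study was completed on 8 February 2021, before this version of 24 November 2021, and the figures would assume a fixed sample size.

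If the formula is kept to describe sampling, reconcile its population (10000 against 11000; 370 against about 371–372) and define the Sample ratio row.

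The cost is wording only: no new patients and no new outcome analysis. The stated precision becomes less favourable, the SAP carries an explicit caveat about stopping, and the sponsor must document how the two groups arose.

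### The SAP uses the observed p-value to confirm its sample size, and presents a stop made after results were seen as a Haybittle-Peto stop with no documented plan

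*SAP*

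**What the plan says.** The SAP, Sample size calculation, applies a finite-population formula to a study population of 10000, Z of 1.96, margin of error 0.05 and proportion 0.5, and concludes "Sample size= 370". It does not say what the 370 counts. The same section reports 539 patients, and the protocol's Study design section splits them 361 (Xagrotin plus standard care) and 178 (standard care).

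The text then turns to results: "To confirm the sufficient sample size of the study, we compared the results of the two groups". It reports a significant difference at below 0.001 without naming an outcome. On Pocock and O'Brien-Fleming it says that each "boundary consider P-value= 0.02 as strength of evidence to stop a trial for benefit", and it continues that "the Haybittle-Peto boundary has shown that if data has a statistical difference at the level of P <0.001" this can count as evidence for stopping early for benefit. The conclusion is "Most of the results of our study had a P-value <0.001 that allowed us to stop sampling", with the added reason that "we ethically needed to stop random sampling in current clinical trial study and publish the results as soon as possible".

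The end of the same section says that collection of new data has continued and that the new data bear out the earlier results. It gives no numbers.

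The protocol's Outcome measures table lists two primary outcomes, 30-day mortality and duration of disease, and one secondary outcome, hospitalization. The SAP header gives primary completion as 7 December 2020 and identifies the text as "Protocol Version 1.4.2: 24- NOVEMBER-2021".

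**The concern.** Two different things are claimed from the same p-value.

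The first is that the sample was big enough. Adequacy is a matter of design: it depends on the effect to be detected, the power and the error rate, all set without reference to the outcome. A significant result from a study of any size would pass the SAP's check, so the check carries no information about size.

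The second is that a recognised sequential boundary permitted the stop. Such a boundary has known error properties only when the endpoint, the looks and the final analysis are fixed beforehand. Here the trigger is most of the results, tied to none of the three listed outcomes.

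At stake is what the trial may claim. As written, a reader would take nominal p-values as the product of a planned group-sequential design, and would take a mortality benefit as part of the reason for stopping, although no document says which outcome reached P <0.001.

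**Working it through.** **1. The plan's own figure.** Inputs from the SAP table: N = 10000, Z = 1.96, e = 0.05, p = 0.5.

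- X = 1.96² × 0.25 / 0.05² = 384.16
- n = 10000 × 384.16 / (9999 + 384.16) = 369.98, so 370 is reproduced.
- With the 11000 eligible patients mentioned in the text, n would be 371.2, so that mismatch hardly matters.

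The formula contains no effect size, power or second group.

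**2. What 370 delivers.**

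- One proportion at p = 0.5, with finite-population correction: 1.96 × √(0.25/370 × 9630/9999) = 0.0500, or 5.0 points.
- Difference between groups of 361 and 178: 1.96 × √(0.25 × (1/361 + 1/178)) = 0.0898, or 9.0 points.

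**3. Was there a planned maximum?** The only stated size is 370.

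- As a total, 539/370 = 1.46, so the sample already exceeded it.
- Per group, 361/370 = 0.98 and 178/370 = 0.48.
- As a figure for the Xagrotin group alone, 361 is close to it.

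The SAP does not say which reading applies, and no maximum for a sequential design is given.

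**4. Does P <0.001 on some outcome speak to mortality?** Take the easiest case, no deaths among 361 on Xagrotin and k among 178 controls, with a two-sided Fisher test.

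- k = 6: p = 0.00122
- k = 7: p = 0.00040

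At least 7 control deaths (7/178 = 3.9%) are needed even with none on Xagrotin. P <0.001 on duration of disease, for example, would not show it for mortality.

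**5. Type I error of the named rule.** Assume one prespecified endpoint, equally spaced looks, P <0.001 at interim looks and 0.05 at the end. Simulation under the null gives about 5.0% to 5.1% for 2 to 5 looks. If P <0.001 were required at every look, including the last, the figure would be 0.19% to 0.37%. Neither is the error of what was done, because the endpoint, looks and final analysis are not recorded.

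**6. Overstatement, for illustration only.** Assume one look and a stop only if two-sided P <0.001 in the favourable direction (c = 3.2905). With true standardised effect μ, the mean estimate among stopped studies divided by the truth is [μ + φ(c − μ)/(1 − Φ(c − μ))]/μ.

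| Power at 0.05 | μ | Factor |
|---|---|---|
| 90% | 3.242 | 1.26 |
| 80% | 2.802 | 1.40 |
| 50% | 1.960 | 1.92 |
| 32% | 1.5 | 2.46 |
| 17% | 1.0 | 3.63 |

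At μ = 5 the factor is 1.02. The true effect is unknown, so these values do not bound the bias.

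**7. The 0.02 figure (minor).** At two-sided 0.05 with equally spaced looks, the Pocock nominal level is 0.0294, 0.0221, 0.0182 and 0.0158 for 2, 3, 4 and 5 looks. O'Brien-Fleming changes from look to look: 0.0052 then 0.0480 with two looks, and 0.0005, 0.0141, 0.0451 with three. A single 0.02 for both methods cannot be checked without the number of looks. The stop itself rests on P <0.001.

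**8. Dates.** 7 December 2020 to 24 November 2021 is 352 days. No date in either document is attached to a look or to the stop.

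**The case against.** The strongest defence is that P <0.001 is a strict threshold. A reader might infer from the missing plan that the false-positive rate was inflated, and the documents do not support that: the Haybittle-Peto rule, properly set up on one endpoint, costs almost nothing over 5%. This part of the defence stands. What cannot be granted is the step from a strict threshold to a known error rate.

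A reader might also infer that no plan ever existed. The text shown is version 1.4.2, so earlier versions may have held one. The documents show only that none is recorded in them, and any request to withdraw the boundary claim must therefore be conditional.

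A third tempting reading is that the trial was cut short. If 370 is a total, 539 exceeds it and nothing was cut short; the documents do not settle this. Nor do they settle whether sampling here means enrolling patients or drawing records of patients already treated. The wider conflict between the retrospective and the randomized descriptions of the study is a separate point.

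Finally, the sponsor gave an ethical reason for stopping: high Covid-19 mortality and results seen as a major advance. That reason may be kept. It explains the decision but does not supply the statistical properties of a boundary.

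**Conclusion.** The point holds in two parts and should be fixed. Using the observed P <0.001 to confirm the sample size is circular, whatever the data show. The Haybittle-Peto justification is undocumented in every element that would give it meaning, and the triggering results are not linked to the listed outcomes. Continued data collection is also left unreconciled with the stated stop.

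The size of the consequence is only partly known. The type I error is indeterminate, and inflation is not shown. The 9.0-point half-width is at p = 0.5, the widest case. The overstatement factors assume a single look and a favourable-result stop; they show direction and possible scale, and no upper limit is known. The mortality threshold of 7 control deaths assumes none on Xagrotin and a two-sided Fisher test.

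**What to change.** 1. Delete the statement that the group comparison confirms the sample size. Describe 370 as a one-proportion precision figure and say whether it is a total, a per-group number or the Xagrotin group only.
2. Unless a dated prospective plan can be cited, withdraw the claim that a Haybittle-Peto, Pocock or O'Brien-Fleming boundary permitted the stop, including the 0.02 sentence. Replace it with a dated correction along these lines: *The sample of 539 was fixed after results had been seen; no prospective stopping boundary is documented; the data were examined [number, dates, endpoints, or not recorded]; p-values are nominal and estimates may be overstated.* The sponsor's stated reason for stopping can remain beside it.
3. Report mortality and duration of disease (primary) and hospitalization (secondary) with effect estimates and confidence intervals, so that each result belongs to a named outcome.
4. Say whether the stop ended enrolment or ended the drawing of records, and reconcile it with continued collection. Either show the later data separately with their numbers or remove the statement that they bear out the earlier results.

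The cost is low: edits to one SAP section, three sets of estimates and, if the later data are kept, one table. No new data are required. The history of looks may not be recoverable, which is why the wording allows for that. The sponsor loses the boundary-based early-stopping claim unless a dated plan is produced, and the correction cannot restore the error control.
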